8.5 Efficacy Analysis

8.5.1 Definition of Efficacy Endpoints

The primary, key secondary and other secondary efficacy endpoints are listed in Section 3.2 and 3.3. This section defines the endpoints themselves and the associated conditions defining loss of those endpoints.

8.5.2 Primary Endpoint Analysis

The primary analysis of the primary endpoint will be performed using a one-sided fisher exact test to compare the proportions of patients with major bleeding during the whole study between the two arms. The significance level is set at 0.05. This primary analysis will be based on the ITT population.

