Prohibited Medications/treatment	Hydroxyurea and procoagulant agents including DDAVP, recombinant FVII or prothrombin complex concentrate are prohibited in patients receiving EACA
Safety Evaluations	Clinical assessment once weekly during the first 30 days and then monthly for 6 months, CBC and bleeding score twice weekly the first 30 days, and then according to standard of care or at discretion of treating physician.
Statistical Analysis	
Population Analysis
 
Intention to treat (ITT) population: The ITT population includes all patients who are randomized to the study. Patients will be stratified and analyzed according to the treatment to which they were assigned.
 
Safety Population: The safety population includes all patients who have received at least 1 dose of EACA. Patients included in the safety population will be analyzed according to the treatment they received.
 
Per-protocol Population: The per-protocol population includes all patients who are randomized, receive at least one dose of study drug, and have no major protocol violations that could be expected to impact response data.
 
Study Endpoints

- **Primary Endpoint:** is to compare at the end of the study, the proportion of patients with major bleeding during the study period among patients randomized to receive either EACA or standard of care prophylactic platelet transfusions.
- **Secondary Endpoints** include:
 - proportion of patients with any bleeding during the study period in each arm
 - the total number of units of platelets transfused in each arm at the end of the study
 - Quality of life as measured in each arm before the study and at the end of the study
 - Safety in each arm

Sample Size

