The primary endpoint is to compare the proportion of patients who develop major bleeding (WHO grade 3 or 4) in each arm.

3.3. Secondary Endpoints:

[figure not shown]
Secondary endpoints include:

- The proportion of patients who develop any bleed in each arm
- The total number of units of platelets transfused in each arm during the study period
- Quality of life as measured by EQ-5D-5L in each arm prior to start treatment and at the end of the study
- Safety in each arm

3.4. Description of Treatment:

Patients will be stratified by expected duration of thrombocytopenia (acute versus chronic), and randomized to receive oral EACA at the dose of 1,000 mg twice daily or the infusion of 1 U of single donor apheresis of platelet when untransfused platelet counts are $< 20 \times 10^9/L$ in the out-patient or $< 10 \times 10^9/L$ in the in-patient, as measured on at least twice weekly CBCs (standard of care for cytopenic patients). Schema of the trial is listed in Figure 3.

Study Schema.

3.5. Randomization:

Patients will be randomized on a 1:1 ratio within each strata (acute vs. chronic) to EACA (Arm B) or standard prophylactic platelet transfusions (Arm A) using a standard randomization table. The study is unblinded.

4. Patient Selection:

4.1. Inclusion Criteria:

- Age > 18 with a hematological malignancy
- Informed consent
- Thrombocytopenia with untransfused platelet counts < 20 x 10⁹/L in the out-patient or in the in-patient setting and one of the following criteria:
 1. Acute thrombocytopenia in patients with hematological malignancies who are in remission and are receiving myelosuppressive consolidation chemotherapy that is expected to induce marrow aplasia for at least 2 weeks; or
 2. Acute or chronic thrombocytopenia in patients with acute leukemia (myeloblastic or lymphoblastic) receiving induction or re-induction chemotherapy that is expected to induce marrow aplasia for at least 2 weeks; or Expected chronic thrombocytopenia in patients with newly diagnosed marrow failure syndromes, myelodysplastic syndromes, aplastic anemia, chronic myelomonocytic leukemia or myelofibrosis; or
 3. Expected chronic thrombocytopenia in patients with relapsed or refractory hematological malignancies; or

4. Hematopoietic stem cell transplant recipients with chronic thrombocytopenia due to chronic GVHD or other causes.

4.2 Exclusion Criteria:

- Acute promyelocytic leukemia
- Patient receiving anticoagulation
- Patient receiving antiplatelet agents

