5.3 Study Duration and End of Treatment

The total estimated duration of the study is up to 3 year, including 14 months to accrue patients with up to 1 year for treatment and follow up for the last patient. Patients will be supplied study drug until they discontinue from the study.

End of treatment is defined when untransfused platelet count recover to $> 30 \times 10^9/L$ on 2 measurements obtained 5 days apart. For patients without platelets recovery, end of treatment will be set at 6 months. At that time patients will be taken off treatment and enter a long-term follow-up period for 2 years.

Subjects that completed treatment due to platelet count recover to $> 30 \times 10^9/L$ on 2 measurements obtained 5 days apart whom developed thrombocytopenia > 30 days of end of study and fulfill the inclusions and exclusion criteria are allowed to be re-enrolled in the study. Subjects without platelet recovery that completed 6 months of treatment are not allowed to be re-enrolled in the study

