8.1 General Considerations

For the purposes of this protocol and all analyses, a month of treatment is defined as 28 days, and will be the same length as a cycle of treatment for both groups.

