8.2 Analysis Population

Intention to treat (ITT) population: The ITT population includes all patients who are randomized to the study. Patients will be analyzed according to the treatment to which they were assigned.

Safety Population: The safety population includes all patients who have received at least 1 dose of EACA. Patients included in the safety population will be analyzed according to the treatment they received.

Per-protocol Population: The per-protocol population includes all patients who are randomized, receive at least one dose of study drug, and have no major protocol violations that could be expected to impact response data, such as: failure to satisfy one or more eligibility criteria, administration of other anti-cancer therapy concurrent with study drug, and administration of incorrect study drug doses. Major protocol violations will be finalized and documented prior to final data analysis.

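### The pooled Fisher test fixed as primary leaves the acute/chronic randomisation factor unused, at a small cost in power; section 8.2 also sets no arm or count for a re-enrolled patient

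*Protocol*

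**What the plan says.** **Randomisation.** Protocol 3.4: "Patients will be stratified by expected duration of thrombocytopenia (acute versus chronic"). Protocol 3.5: "Patients will be randomized on a 1:1 ratio within each strata (acute vs. chronic").

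**Primary test.** Protocol 8.5.2 has the primary analysis "performed using a one-sided fisher exact test to compare the proportions of patients with major bleeding during the whole study between the two arms", at 0.05, in the ITT population. The synopsis fixes the same test, and 8.4 sizes the trial on it. Section 8.8 lowers the final one-sided level to 0.043 after three looks at 0.001, 0.004 and 0.019. Acute/chronic is not named among the subgroups in 8.5.3 either.

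**ITT wording.** Synopsis: "Patients will be stratified and analyzed according to the treatment to which they were assigned". Section 8.2: "Patients will be analyzed according to the treatment to which they were assigned". The first mentions stratification and the second does not; neither names a stratified test.

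**Time at risk.** Treatment ends at platelet recovery. Otherwise, under 5.3, "For patients without platelets recovery, end of treatment will be set at 6 months", and under 8.1 "a month of treatment is defined as 28 days", so the cap is 6 × 28 = 168 days, or 24 weeks.

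**Re-enrolment.** Section 5.3 lets patients whose platelets recovered enter again if they meet the criteria. Section 6.4 describes randomisation without mentioning a returning patient. Section 8.2 speaks of the assigned treatment as if each patient had one. Sections 8.3.1, 8.5.2 and 8.8 count bleeding over the study without saying whether a later course is included.

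**The concern.** A factor is normally chosen for stratified randomisation because it is expected to predict outcome. Here the route is plausible: the endpoint is whether a patient ever has a major bleed, and a patient treated for longer has more time to have one. A test that ignores such a factor remains valid but becomes more conservative than it need be, and some power is given up at no saving in patients.

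Re-enrolment raises a separate question. Fisher's test takes each patient once, in one arm. A patient randomised first to one arm and later to the other has no single ITT arm under 8.2, and the protocol does not say whether the second entry fills one of the 100 places or counts toward an interim fraction. In an open-label trial that rule should be set before outcomes are compared.

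**Working it through.** **Inputs.** From 8.4: 8% (EACA) v 30% (platelets), one-sided Fisher, 45 per arm, 50 after 10% drop-out. From 8.5.2 and 8.8: levels 0.05 and 0.043. The protocol gives no risks by stratum, so those below are assumptions.

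**1. The plan's own figure.** Power is the sum of Bin(x; n, 0.08) × Bin(y; n, 0.30) over all tables whose one-sided hypergeometric p-value is at or below the level.

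| n per arm | 0.05 | 0.043 |
|---|---|---|
| 44 | 79.0% | – |
| 45 | 80.05% | 77.5% |
| 50 | 84.5% | 82.5% |

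So 45 is the smallest n that reaches 80% at 0.05, and 45/0.9 = 50. The stated design reproduces at 0.05, though not at the level used for the final analysis.

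**2. Pooled v stratified, 50 per arm.** The stratified exact p-value is P(T₁ + T₂ ≤ t | m₁, m₂). T₁ and T₂ are independent hypergeometric counts of EACA events, given the total events m₁ and m₂ in each stratum. Power is by full enumeration with equal strata, a common odds ratio and an EACA average of 8%.

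| Control risk by stratum | Gain at 0.05 | Gain at 0.043 |
|---|---|---|
| 30/30% | 0.1 points | 0.2 points |
| 20/40% | 0.8 | 1.1 |
| 15/45% | 1.6 | 2.0 |
| 10/50% | 2.6 | 2.8 |

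The largest size over null risks of 2% to 58% is 3.3% pooled and 3.4% stratified at 0.05, and 2.8% and 2.9% at 0.043. At 45 per arm with strata alike, the stratified test has 80.2% at 0.05 and 77.9% at 0.043.

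**3. With the interim looks** at 11, 25, 37 and 50 per arm and the levels of 8.8, power goes from 83.1% (pooled) to 83.2% (stratified) at 30/30%, and from 84.7% to 87.4% at 10/50%. Overall size is at most 3.3% for both.

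**4. What stratum risks are plausible?** Assume the same weekly bleeding rate λ in both strata, so that risk = 1 − exp(−λ × weeks), with the two risks averaging 30%.

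- Chronic at the 24-week cap, acute 4 weeks: λ = 0.0283, giving 1 − exp(−0.113) = 10.7% and 1 − exp(−0.679) = 49.3%. The gain is 2.4 points (0.05) or 2.7 (0.043).
- Chronic at 47 days, the median EACA duration in Table 2 (47/7 = 6.7 weeks), acute 4 weeks: λ = 0.0674, giving 23.6% and 36.4%. The gain is 0.39 or 0.57.
- Chronic at 47 days, acute 6 weeks: the gain is 0.13 or 0.19.

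**5. Re-enrolment** (repeat numbers assumed).

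- If 10 of the 100 places are repeats, 90 distinct patients remain, 45 per arm: 80.05% (77.5% at 0.043). With 10% drop-out as well, 45 × 0.9 ≈ 40 per arm: 75.8% (73.0%).
- If 10 repeats come on top of 100 patients, power is 84.5% on the first-course outcome. On an any-course outcome it is 87.0–88.3% if the arm is kept, and 80.6–81.2% if patients are re-randomised but credited to the first arm.
- If same-arm repeats were counted as new patients at 30% risk, size at nominal 5% passes 5% only with many repeats and high within-patient correlation: 5.1% with 20 repeats per 100 and latent correlation 0.9, and 5.6% with 30 repeats and correlation 0.6. With 10 repeats it reaches about 4.0% even at latent correlation 0.9.

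**The case against.** **The pooled test is a legitimate choice.** It is valid, and it is the test the sample size was built on. This stands, and nothing here calls the test wrong. A reader might infer that ignoring the stratification factor invalidates the test or leaves the trial short of its stated power; the enumeration shows neither.

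**The gain may be trivial.** This stands in large part. The gains of 2 points and more need steep assumed splits or every chronic patient at the 24-week cap, whereas treatment may stop earlier under 5.3 and 5.4. Median EACA exposure in the preliminary series was 47 days. Nor does the aplasia criterion in 4.1 ("receiving myelosuppressive consolidation chemotherapy that is expected to induce marrow aplasia for at least 2 weeks") mark out the acute stratum: two weeks is a minimum, and the second criterion applies the same expectation to acute or chronic thrombocytopenia.

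**The synopsis and 8.2 barely differ.** Agreed. The synopsis names neither the factor nor a stratified test, so this is a wording mismatch and not a contradiction about the analysis.

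**Changing a primary test late in an unblinded trial carries risk.** This stands, and it limits the fix: the change is acceptable only before a comparison by arm has been seen.

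**Counting patients already implies one entry each, and the rest is SAP detail.** Partly right. A count of patients does favour one entry, and 5.3 with 6.4 suggests that a returning patient is randomised again. But the protocol itself fixes the ITT rule and itself permits re-enrolment, and together they leave no single arm for a patient assigned twice.

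**Type I error under re-enrolment.** A reader might infer that excluding a history of grade 4 bleeding (4.2) removes any risk of inflation. It does not: grade 3 is also a primary event, and a patient whose grade 3 bleed has resolved is not barred by that criterion. The opposite inference, that inflation is general, is not supported either.

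**Conclusion.** The point holds as a modest improvement. The fixed primary test does not use the factor on which randomisation is stratified. An exact stratified test would keep size below nominal and add about 0.1 to 2.6 points of power at 50 per arm and 0.05 (0.2 to 2.8 at 0.043). The lower end is the more likely if exposure resembles the preliminary series: 0.1 to 0.4 points, or 0.2 to 0.6. These figures rest on assumed stratum risks, equal strata, a common odds ratio and, for the exposure-based range, an assumed 4 to 6 weeks of acute treatment with one weekly bleeding rate.

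The re-enrolment gap is real but secondary. Depending on the rule chosen and the number of repeats, power moves by several points in either direction. Size could slightly exceed 5% only if same-arm repeats were counted twice, were numerous and were highly correlated. The protocol gives no expected number of repeats.

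**What to change.** - **8.5.2 and synopsis:** make the primary comparison a one-sided exact test stratified by acute/chronic thrombocytopenia, in the ITT population, at the levels of 8.8. Keep the pooled one-sided Fisher test as a sensitivity analysis.
- **8.8:** use the same test at every remaining look and at the final analysis.
- **Timing:** date the amendment before any comparison by arm is seen. If one has been seen, keep pooled Fisher as primary and report the stratified test as supportive.
- **8.2:** state that each patient counts once in the primary ITT analysis, in the arm and stratum of the first randomisation, and that repeat courses do not count toward the 100 patients or the interim fractions. Align the ITT wording with the synopsis.
- **6.4:** state whether a returning patient is randomised again.
- **8.3.1, 8.5.2 and 8.8:** reconcile which courses count. If only the first course counts, say that this narrows the present whole-study wording, and report the any-course outcome, credited to the first arm, as a sensitivity analysis.

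**Cost.** One dated amendment to the primary analysis of an open-label trial already at Amendment 5. The stratified test needs no extra patients. Accrual may take longer if repeats no longer fill places.

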8.5.3 Secondary Endpoint Analysis

One-sided t-test will be used to compare the total number of bleeding episodes noted during the study between the two arms. Two-sided t-test will be employed to compare the total number of units of platelets transfused at the end of the study between the two arms. Appropriate statistical tests (Chi-square test, t-test, Wilcoxon's rank sum test, etc.) will be conducted to compare the each score of the quality of life between the two arms before the study and at the end of the study, respectively. The change of each score of the quality of life from before the study to the end of the study will also be compared between the two arms. The safety in each arm will be also compared with Fisher's exact test. The analyses of secondary endpoints will be performed on the ITT population and the significance level will be kept at 0.05 for all tests.

For the primary and secondary efficacy endpoints, subgroup analyses will be performed by baseline potential prognostic factors. Subgroups will include: age, gender, race, underlying diagnosis, and other disease-related prognostic factors (disease status).

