This randomized, open-label phase II study is designed to compare proportion of patient with major bleedings ever noted during the study. Patients will be assigned to receive prophylactic EACA (experimental arm) or prophylactic platelet (standard of care) in a 1:1 fashion. Previous studies suggest that the proportions of patients with major bleeding will be expected to be 8% and 30% in experimental arm and standard of care arm, respectively. With one sided Fisher's exact test, the sample size of 45 patients in each arm will achieve a power of 80% at the significance level of 5% to test whether prophylactic EACA can prevent major bleeding better than the standard of care. After adjusting for a 10% drop out rate, the actual required sample size will be 50 patients per arm. Therefore, the total sample size of the study will be 100 patients.

Efficacy Analysis

- **Primary Endpoint Analysis** will be performed using a one-sided fisher exact test to compare the proportions of patients with major bleeding during the whole study between the two arms. The significance level is set at 0.05. This primary analysis will be based on the ITT population.
- **Secondary Endpoint Analysis:** one-sided t-test will be used to compare the total number of any bleeding episode noted during the study between the two arms. Two-sided t-test will be employed to compare the total number of units of platelets transfused at the end of the study between the two arms. Appropriate statistical tests (Chi-square test, t-test, Wilcoxon's rank sum test, etc.) will be conducted to compare the each score of the quality of life between the two arms before the study and at the end of the study, respectively. The change of each score of the quality of

life from before the study to the end of the study will also be compared between the two arms. The safety in each arm will be also compared with Fisher's exact test. The analyses of secondary endpoints will be performed on the ITT population and the significance level will be kept at 0.05 for all tests.

Safety Analysis

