1.4 Rationale for the Conduct of this Study

Given the high incidence of platelet refractoriness, and the prolonged duration of thrombocytopenia in patients with hematological malignancies and marrow failure syndromes, alternatives to platelet transfusions are desperately needed. Our institutional experience with EACA provides a unique expertise to further investigate the role EACA can play in the prevention of bleeding in this patient population. We therefore propose to conduct a prospective, randomized, controlled trial to compare EACA versus standard prophylactic platelet transfusion to prevent bleeding in thrombocytopenic patients with hematological malignancies. The objectives of the trial are to address safety and efficacy of EACA as assessed by major and minor bleeding, cumulative platelet transfusion consumption, quality of life and costs in both arms of the study.

Table 2: Characteristics of 44 thrombocytopenic patients who received epsilon aminocaproic acid for the prevention of bleeding

Age, years median (range)	61 (17-82)
Male/female	29/15
Platelet counts $\times 10^9/L$ when EACA started, median (range)	8 (1 – 19)
Patients with platelet refractoriness n (%)	10 (23%)
Duration of thrombocytopenia in days, median (range)	273 (20-1463)
Diagnosis n (%)	
CML	9 (21)
AML	14 (32)
ALL	1 (2)
MDS	15 (35)
CLL	1 (2)
ITP	1 (2)
Lymphomas	1 (2)
Aplastic anemia	1 (2)
Myelofibrosis	1 (2)
Disease Status of patients at the time EACA started	
Active treatment, n (%)	13 (29)
Relapsed/refractory, n (%)	31 (71)
Duration of EACA therapy, median(range) in days	47 (7-209)
Patients without bleeding on EACA, n (%)	26 (59)
Patients with bleeding episodes while on EACA, n (%)	18 (41)
Patients requiring platelet transfusions for bleeds, n (%)	7 (16%)
Grade and location of the 10 bleeding episodes requiring platelet transfusions:	
Grade 4 – CNS*	1

Grade 3 – rectal	1
Grade 2 – hemorrhoids	1
Grade 2 – hematuria **	2
Grade 2 – epistaxis	1
Grade 2 – oral	3
Grade 2 – vaginal	1
Grade and location of the 19 bleeding episodes not requiring platelet transfusions:	
Grade 1- epistaxis	7
Grade 1 – skin bruises	4
Grade 1 – gingival bleed	2
Grade 1 - vaginal	1
Grade 2 – gingival	2
Grade 2 – vaginal	1
Grade 2 - epistaxis	2
Reason for discontinuing EACA, n (%)	
Death	25 (57)
Increased platelets count	18 (41)
Hematuria	1 (2)

*Traumatic brain injury in a car accident

**One patient had 2 episodes of hematuria

2 Study Objectives and Hypothesis

2.1 Primary Objective:

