The primary objective of this study is to compare the proportion of patients who develop major bleeding episodes (WHO grades 3-4) in the group randomized to receive prophylactic EACA versus standard of care prophylactic platelet transfusions.

2.2 Secondary Objectives:

- To compare the proportion of patients who develop any bleeding episode in the group randomized to receive prophylactic EACA versus standard of care prophylactic platelet transfusions.
- To compare, according to treatment with prophylactic EACA or prophylactic platelet transfusions, the total number of units of platelet transfused
- To compare the quality of life in both arms of the study

2.3 Hypothesis:

This is a non-inferiority trial in which we hypothesize that in thrombocytopenic patients with hematological malignancies, comparable incidence of bleeding will be observed with the prophylactic use of EACA and standard of care arm prophylactic platelet transfusions.

3 Investigational Plan

3.1 Overall Study Design and Plan:

This is a single center, randomized phase 2, open label trial of oral EACA versus platelet transfusions for the prevention of bleeding in thrombocytopenic patients with hematological malignancies.

Eligible patients with acute or chronic thrombocytopenia will be randomized in a 1:1 fashion to receive oral EACA at the dose of 1,000 mg twice daily as a substitute for prophylactic platelet transfusions or standard of care prophylactic platelet transfusions for an untransfused platelet count $< 20 \times 10^9/L$ in the out-patient or in the in-patient setting. Patients will be assessed twice weekly and as needed in between visits for the presence of bleeding. The number of platelets transfused for prophylaxis (arm B) or for therapeutic purposes (both arms) will be monitored. Patients will complete quality of life questionnaire. Adverse events will be assessed and graded according to the National Cancer Institute Common Terminology Criteria for Adverse Events (CTCAE) version 4.0. Bleeding will be assessed and graded according to the World Health Organization (WHO) classification [Appendix 1]. Patients will be assessed according to a protocol-specific schedule of events. Patients will continue treatment on trial until one or more criteria for discontinuation are met. Patients will be supplied with study drug until they discontinue from the study. Patients will be followed for 2 years or death, whichever occurs first.

3.2. Primary Endpoint:

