8.3.2 Secondary Endpoint

Secondary endpoints include:

- proportion of patients with any bleeding during the study period in each arm
- the total number of units of platelets transfused in each arm at the end of the study
- Quality of life as measured by in each arm before the study and at the end of the study
- Safety in each arm

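### The first secondary endpoint is the proportion of patients with any bleeding, but the only secondary bleeding test planned is a one-sided t-test on episode totals

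*Protocol*

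**What the plan says.** Four places define the first secondary bleeding outcome per patient, as yes or no:

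- 2.2 Secondary Objectives: "To compare the proportion of patients who develop any bleeding episode in the group randomized to receive prophylactic EACA", against standard prophylactic platelets.
- 3.3 Secondary Endpoints: "The proportion of patients who develop any bleed in each arm".
- 8.3.2 and the synopsis endpoint list: "proportion of patients with any bleeding during the study period in each arm".

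Section 8.5.1 ties the efficacy analysis to those lists: "The primary, key secondary and other secondary efficacy endpoints are listed in Section 3.2 and 3.3". Neither 3.2 nor 3.3 lists an episode count.

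The analysis text tests a count. Section 8.5.3 states: "One-sided t-test will be used to compare the total number of bleeding episodes noted during the study between the two arms". The synopsis, under Efficacy Analysis, says the same: "one-sided t-test will be used to compare the total number of any bleeding episode noted during the study between the two arms". Section 8.5.3 also sets the ITT population and the 0.05 level for the secondary endpoints.

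**The concern.** A proportion of bleeders and a mean number of episodes answer different questions. The first asks how many patients bleed at all; the second also weighs how often each bleeder bleeds again. A treatment can change one and not the other.

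Followed as written, the plan would show the two any-bleeding proportions without a test and attach a p-value to the episode totals. A reader would naturally take that p-value as the result for the declared endpoint. An analyst who tested the proportion instead would depart from 8.5.3. In an open-label trial, that leaves room to choose between two bleeding measures after the results are known.

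A smaller point is that raw totals ignore time at risk. Under 5.3, treatment ends at platelet recovery, and "For patients without platelets recovery, end of treatment will be set at 6 months". Observation can therefore run from weeks to months.

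**Working it through.** **1. Does any other test cover the declared endpoint?** The planned tests, side by side:

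| Place | Test | Applies to |
|---|---|---|
| 8.5.2 | one-sided Fisher | proportion with major bleeding |
| 8.5.3 | one-sided t-test | total bleeding episodes |
| 8.5.3 | two-sided t-test | platelet units |
| 8.5.3, 8.7 | chi-square, t-test or Wilcoxon | quality-of-life scores |
| 8.5.3 | Fisher | safety |
| 8.6 | two-sided chi-square or t-test | AE incidence and toxicity |

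None is assigned to the proportion with any bleeding. A t-test can be run on a 0/1 variable, but both analysis texts speak of a total number of episodes. Section 8.5.2 shows that the Protocol writes of proportions when it means them.

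**2. Do the two quantities differ in this population?** Table 2 in section 1.4 reports 44 patients on EACA, of whom 18 bled. Ten episodes needed platelets, and a second list is headed "Grade and location of the 19 bleeding episodes not requiring platelet transfusions".

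- Any bleeding: 18/44 = 41%.
- Episodes: 10 + 19 = 29.
- Per bleeder: 29/18 = 1.61.
- Per patient: 29/44 = 0.66.

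Repeat bleeding is common enough for the two measures to separate.

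**3. The plan's own figure.** The Protocol gives no power or control rate for any bleeding. Its only sample-size figure concerns major bleeding (8% vs 30%, one-sided Fisher, 5%). Exact enumeration gives 80.05% power at 45 per arm, and 45/(1 − 0.10) = 50. That figure reproduces and is not in question.

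**4. How far can the conclusions diverge?** Set-up: 50 per arm, one-sided 5%, 40,000 simulated trials per scenario (Monte Carlo standard error at most 0.0025). A patient bleeds with probability p. A bleeder has 1 + extra episodes, with mean m in total and extras either Poisson or geometric. Mean episodes per patient = p × m. The 41% and 1.61 come from Table 2; every difference between arms is an assumption. The t columns give Poisson / geometric.

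| Scenario (EACA vs control) | p × m | t-test significant | Fisher significant |
|---|---|---|---|
| p 41% both, m 1.61 both | 0.66 vs 0.66 | 5.1% / 5.0% | 3% |
| p 41% both, m 1.3 vs 2.0 | 0.53 vs 0.82 | 42% / 35% | 3% |
| p 25% vs 50%, m 2.64 vs 1.32 | 0.66 vs 0.66 | 7% / 9% | 78% |
| p 41% vs 60%, m 1.61 both | 0.66 vs 0.97 | 47% / 43% | 51% |

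In the last row, the two tests disagree on significance in 19% (Poisson) or 23% (geometric) of trials. The first row shows that the t-test holds its level. It is valid for mean counts; the fault is that mean counts were not declared.

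**5. Time at risk.** This is an assumed model, since the Protocol does not show that observation differs by arm. Episodes are gamma-Poisson (dispersion 1) with mean 29/44. Observation days are lognormal with median 47 and log-SD 0.8, clipped to 7-168. Bleeding rates are equal, and EACA patients are observed for less time:

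| Less observation on EACA | 0% | 2% | 5% | 10% | 20% | 30% |
|---|---|---|---|---|---|---|
| t-test rejects | 4.7% | 5.5% | 6.5% | 8.5% | 14% | 23% |
| Fisher rejects | 3.3% | 3.6% | 4.1% | 5.4% | 8.7% | 14% |

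The crude proportion is also affected, though less.

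**The case against.** **Naming a test for a secondary proportion can be left to the SAP.** Section 2.2 already states the comparison, and 8.5.3 fixes population and level. That would answer a silent protocol. This one is not silent: it fixes a test, a direction and a level for a quantity it never declares, so an SAP must contradict either 8.5.3 or 2.2. What stands is a matter of wording: the named test is missing, not the intention to compare.

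**The large divergences are constructed.** This stands in part. Nothing in the Protocol suggests 1.3 vs 2.0 episodes per bleeder, or that EACA halves the bleeders while doubling their repeats. With 1.5 vs 1.7 and equal proportions of 41%, the t-test is significant in only 10-11% of trials. In the 41% vs 60% scenario the power of the two tests is close. Some disagreement there is ordinary: Fisher and an uncorrected one-sided z-test of the same proportions disagree in 8% of trials. Even so, 19-23% is well above that and needs no difference in repeat bleeding.

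**The time-at-risk figures rest on assumption.** They do. The 47-day median is EACA treatment time in a series where 57% stopped because of death, and a test of proportions does not remove the bias. These figures add little weight to the main point.

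**A rate model needs more than the Protocol gives.** This stands too. Bleeding is graded by visit, after day 30 the schedule follows standard of care, and no rule says where one episode ends.

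**Conclusion.** The concern holds. The contradiction can be read directly from 2.2, 3.3, 8.3.2 and 8.5.1 against 8.5.3, with the synopsis repeating both sides, and it does not depend on simulation. The simulations show only that the choice can change the conclusion; their size rests on assumed arm differences and assumed distributions of repeat bleeding. The damage is confined to one secondary endpoint. The primary test and the sample size are unaffected. This should be corrected, but it does not threaten the trial's main result.

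**What to change.** In 8.5.3 and the synopsis, state that the proportion of patients with any bleeding is compared between arms with Fisher's exact test in the ITT population, as 8.5.2 does for major bleeding.

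Then either drop the episode count or list it as its own additional endpoint in 3.3 and 8.3.2. If it is kept, define an episode and analyse the count as a rate over days under observation, for example by negative binomial regression with a log-time offset, instead of a t-test on raw totals. The offset adjusts for duration, not for uneven frequency of assessment. Report days under observation by arm beside both results, because the crude proportion also depends on them.

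The cost is wording in 8.5.3 and the synopsis, plus a line in 3.3 and 8.3.2 and an episode definition if counts stay. The yes/no endpoint needs no new data, and the sample size does not change.
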